9.1 General

In the case that adverse events related to the study intervention are reported, these will be recorded per the descriptions and grading scales found in the revised National Cancer Institute Common Terminology Criteria for Adverse Events (CTCAE) Version 4.0 for adverse event reporting that can be found at <http://ctep.cancer.gov/reporting/ctc.html>.

Information about all intervention-related adverse events, including those volunteered by the subject verbally or reported by the patient on the tCDS side effect questionnaire, discovered by investigator/study personnel questioning, or detected through other means, will be collected, followed, and reported appropriately.

Only adverse events thought to be related to tDCS will be collected, tracked and reported (as per section 9.2.4 on attribution). The adverse events related to any ongoing treatment for the patients' other medical conditions, including breast cancer, will not be collected.

All adverse events experienced by subjects will be collected from the time of first administration of tDCS (active or sham), throughout the study and until the final study visit. Subjects continuing to experience toxicity believed to be related to tDCS after discontinuation of the study may be contacted for additional assessments until the toxicity has resolved or is deemed irreversible.

9.2 Definitions

9.2.1 Adverse event (AE): An adverse event is any undesirable sign, symptom or medical condition occurring after starting study drug (or therapy) even if the event is not considered to be related to the study.

Medical conditions/diseases present before starting study treatment are only considered adverse events if they worsen after starting study treatment (any procedures specified in the protocol).

Abnormal laboratory values or test results constitute adverse events only if they induce clinical signs or symptoms or require therapy.

9.2.2 Serious adverse event (SAE): A serious adverse event is an untoward sign, symptom, or medical condition which:

- results in death;
- is immediately life-threatening;
- requires inpatient hospitalization or prolongation of existing hospitalization;
- results in persistent or significant disability/incapacity;
- is a congenital anomaly/birth defect;
- jeopardizes the subject and requires medical or surgical intervention to prevent; or one of the outcomes listed above.

The definition of serious adverse event (experience) also includes *important medical event*. Medical and scientific judgment should be exercised in deciding whether expedited reporting is appropriate in other situations, such as important medical events that may not be immediately life-threatening or result in death or hospitalization but may jeopardize the subject or may require intervention to prevent one of the other outcomes listed in the definition above. These should also usually be considered serious. Examples of such events are intensive treatment in an emergency room or at home for allergic bronchospasm; blood dyscrasias or convulsions that do not result in hospitalization; or development of drug dependency or drug abuse.

Events **not** considered to be serious adverse events are hospitalizations for:

- routine treatment or monitoring of the studied indication, not associated with any deterioration in condition, or for elective procedures
- elective or pre-planned treatment for a pre-existing condition that did not worsen
- emergency outpatient treatment for an event not fulfilling the serious criteria outlined above and not resulting in inpatient admission
- respite care

A hospitalization planned before the start of study participation) and/or for a preexisting condition that has not worsened does not constitute a serious adverse event. A hospitalization for a social reason in the absence of an adverse event also does not meet the criteria for a serious adverse event.

The following events will also require expedited reporting for this protocol, similar to those events meeting the definition of SAE above:

- a female subject becomes pregnant while receiving investigational therapy, the pregnancy must be reported; follow-up to obtain the outcome of the pregnancy should also occur;
- abortion, whether accidental, therapeutic, or spontaneous, should additionally always be classified as serious, and expeditiously reported;
- exposure of a baby during lactation to study treatment

9.2.3 Expectedness

- Unexpected adverse event: An adverse event is considered unexpected when it varies in nature, intensity or frequency from information provided in the current adverse event list, the Investigator's Brochure, the package insert or when it is not included in the informed consent document as a potential risk
- Expected (known) adverse event: Expected adverse events are those that have been previously identified as resulting from administration of the agent. For the purposes of this study, an adverse event is considered expected when it appears in the current device manual or is included in the informed consent document as a potential risk.

9.2.4 Attribution

The relationship of all adverse events and serious adverse events to the study intervention will be assessed by an investigator and assigned as follows:

- Definite: The AE is clearly related to the study treatment. An adverse event which has a timely relationship to the administration of the investigational intervention, follows a known pattern of response, for which no alternative cause is present.
- Probable: The AE is likely related to the study treatment. An adverse event, which has a timely relationship to the administration of the investigational intervention, follows a known pattern of response, but for which a potential alternative cause may be present.
- Possible: The AE may be related to the study treatment. An adverse event, which has a timely relationship to the administration of the investigational intervention, follows no

known pattern of response, but a potential alternative cause does not exist.

- Unlikely: The AE is doubtfully related to the study treatment. An adverse event which does not have a timely relationship to the administration of the investigational intervention, follows no known pattern of response, does not reappear or worsen after re-administration of the investigational intervention (if applicable), and for which there is evidence that it is related to a cause other than the investigational agent.
- Unrelated: The AE is clearly NOT related to the study treatment. An adverse event, for which there is evidence that it is definitely related to a cause other than the investigational intervention. In general, there is no timely relationship to the administration of the investigational intervention, or if there is a timely relationship, the event does not follow a known pattern of response, and there is an alternative cause.

Only adverse events which are definitely, probably or possibly related to tDCS will be tracked, recorded and reported for this study.

9.3 Reporting Procedures

9.3.1 General

All adverse events will be captured on the appropriate study-specific case report forms (CRFs).

9.3.2 Serious Adverse Events

All serious adverse events, regardless of causality to study intervention, will be reported to the Principal Investigator.

9.3.3 Institutional Review Board

All adverse events and serious adverse events will be reported to the IRB per current institutional standards. If an adverse event requires modification of the informed consent, these modifications will be provided to the IRB with the report of the adverse event. If an adverse event requires modification to the study protocol, these modifications will be provided to the IRB as soon as is possible.

10. DATA AND SAFETY MONITORING

10.1 Data Management

All information will be collected on study-specific case report forms by the study staff. In the event that an electronic database is used, the following procedures will apply:

- The database will be password protected; only authorized staff may enter and view study data.
- Passwords and system IDs will not be shared.
- Physical security of the workstations/files will be maintained.
- Staff is trained on the data entry system and importance of security procedures.
- Workstations with the database open will not be left unattended.

All study data will be reviewed for completeness and accuracy by the Principal Investigator. The study data may also be periodically reviewed by the Sidney Kimmel Comprehensive Cancer Center Clinical Research Office.

10.2 Meetings

The study staff will schedule meetings, as needed, depending on the rate of accrual, and will include the Protocol Chair, Co-Chair, and the following study team members as appropriate: study coordinators, data managers, research nurses, sub-investigators, collaborators (if applicable), and statistician.

During these meetings matters related to the following will be discussed: enrollment rate relative to expectation, characteristics of participants, retention of participants, adherence to protocol (potential or real protocol violations), validity and integrity of the data, safety data, analysis of samples, and progress of data for objectives.

10.3 Monitoring

This is a Level I study under the SKCCC Data Safety Monitoring Plan. The principal investigator is responsible for internally monitoring the study and establishing additional external data and safety monitoring oversight, as required. The principal investigator will also monitor the progress of the trial, review safety reports, and confirm that the safety outcomes and response assessments favor continuation of the study.

The study involves a device, NeuroConn DC Stimulator Plus Model 0021, that meets the criteria for non-significant risk (NSR) for which an IDE from the FDA is not required for the clinical trial outlined ⁸⁹.

This study will be monitored per the SKCCC Data Safety Monitoring Plan. The Clinical Research Office QA Group will perform an audit as the specified intervals. All trial monitoring and reporting will be reviewed at least annually by the SKCCC Safety Monitoring Committee.

11. ADMINISTRATIVE PROCEDURES

11.1 Protocol Amendments

Any changes to the protocol will be made in the form of an amendment and must be approved by the IRB before implementation. The Principal Investigator (or her designee) is responsible for the coordination and development of all protocol amendments, and will disseminate this information to the participating centers.

11.2 Informed Consent

Those members of the research team (principal investigator, co-investigator, research staff) who consent patients have been trained in informed consent procedures, are familiar with the protocol, and are listed as a consenter in the application document. Patients are given adequate time and privacy to consider the research study. Before the patient signs the consent, the consenter must be satisfied that the participant understands the information provided, has had an opportunity to discuss the information and ask questions, and is aware that he/she may withdraw from the study at any time.

The investigator (or her designee, as appropriate) will explain to each subject the nature of the study, its purpose, procedures involved, expected duration, potential risks and benefits. Each subject will be informed that participation in the study is voluntary and that she may withdraw from the study at any time, and that withdrawal of consent will not affect her subsequent medical treatment. This informed consent will be given by means of a standard written statement and will be submitted for IRB approval prior to use. No patient will enter the study before her informed consent has been obtained.

In accordance with the Health Insurance Portability and Accountability Act (HIPAA), the written informed consent document (or a separate document to be given in conjunction with the consent document) will include a subject authorization to release medical information to the study sponsor and supporting agencies and/or allow these bodies, a regulatory authority, or Institutional Review Board access to subjects' medical information that includes all hospital records relevant to the study, including subjects' medical history.

11.3 Ethics and Good Clinical Practice

This study must be carried out in compliance with the protocol and Good Clinical Practice, as described in:

- ICH Harmonized Tripartite Guidelines for Good Clinical Practice 1996
- US 21 Code of Federal Regulations dealing with clinical studies (including parts 50 and 56 concerning informed consent and IRB regulations)
- Declaration of Helsinki, concerning medical research in humans (Recommendations Guiding Physicians in Biomedical Research Involving Human Subjects, Helsinki 1964, amended Tokyo 1975, Venice 1983, Hong Kong 1989, Somerset West 1996)

The investigator agrees to adhere to the instructions and procedures described in it and thereby to adhere to the principles of Good Clinical Practice.

12. STATISTICAL CONSIDERATIONS

12.1 Overall

- 12.1.1 The primary outcome measure will be performance on the PASAT. Specifically, our primary hypothesis is that anodal tDCS will result in greater offline (i.e. post-versus pre-stimulation) improvement in objective cognitive test scores after multiple days than does sham stimulation. Our primary outcome variable reflects the difference between pre- and post-anodal stimulation compared to pre- and post-sham stimulation, or [(score before anodal minus score after anodal)-(score before sham minus score after sham)].
- 12.1.2 Our secondary outcome measures will be subjectively rated fatigue and cognitive functioning as indexed by scores on the MFSI-SF and FACT-Cog. Specifically, our primary hypothesis is that anodal tDCS will result in greater offline (i.e. post-versus pre-stimulation) improvement in subjective fatigue and cognition after multiple days than does sham stimulation. Our secondary outcome variables reflects the difference between pre- and post-anodal stimulation compared to pre- and post-sham stimulation, or [(score before anodal minus score after anodal)-(score before sham minus score after sham)].
- 12.1.3 Exploratory outcome measures will include scores on other objective cognitive tests; disease-, treatment- and person-related predictors of response to tDCS intervention; and side effects of active and sham tDCS intervention as outlined above.

12.2 Sample Size and Accrual

The proposed study is a randomized, sham-controlled, double-blind, cross-over experiment. Each participant will receive five consecutive days of active tDCS and five consecutive days of sham stimulation in a random order, with a 4 to 5-week washout period in between. The primary endpoint is the difference in PASAT score before and after active/sham tDCS. The effect of tDCS in working memory performance will be evaluated by comparing the change in PASAT score before and after tDCS with that before and after sham stimulation. The null hypothesis is that tDCS usage will yield the same mean change in PASAT score as the sham stimulation.

Our accrual goal is to have 45 patients complete the crossover experiments with both active and sham tDCS. In the multiple sclerosis literature studies with a similar design have reported an attrition rate of approximately 10%³³⁻³⁵. Hence, to achieve the target accrual, we expect to enroll 50 breast cancer patients, with the expectation that 5 may not complete the crossover experiments. This sample size (n=45) will yield at least 80% power to detect a medium effect size (Cohen's d) of 0.43 or greater at a two-sided type I error rate of 5% using paired t-test.

12.3 Analysis Plan

The comparison between active tDCS and shame stimulation in change in PASAT score will be performed using a two-sided paired t-test based on data from participants who complete the crossover experiments. We will also use a linear mixed effects model to evaluate the effect of tDCS in the change in PASAT score by including data from all participants who complete at least one study wave.

For secondary and exploratory endpoints, pre- and post-stimulation scores, including scores on the PASAT, FACT-Cog, and MFSI-SF, and the corresponding changes in scores (post-pre) after five consecutive days of stimulation will be summarized using descriptive statistics and displayed graphically for each stimulation condition. Data may be transformed as appropriate to reduce skewness and improve symmetry. To account for correlation among multiple measurements within the same patient, linear mixed effects models will be used to evaluate the effect of tDCS, where the outcome is the change in scores (post-pre stimulation) and the covariates will include the indicator of the stimulation condition. Other covariates in the exploratory analyses may include but not be limited to the order of the experiments (for assessing carryover effects), number of days receiving active/sham stimulations, baseline fatigue, depression, anxiety, loneliness, handedness, cancer stage, and cancer treatment. The change in MFSI-SF and FACT-Cog score obtained (via phone) seven days after each study wave will be analyzed using the same approach. Exploratory sensitivity analyses will be carried out to examine if dropout/missingness is informative.

Data analyses will be performed by the study statistician, [name].

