7.4 Randomization and Blinding

Upon eligibility confirmation and study registration, participants will be randomized to receive active or sham tDCS during the first five-day study wave (to be followed by the opposing condition in the second five-day study wave). This is a double-blind study. Both the participant and study team members will remain blinded to the application of active or sham tDCS throughout the course of an individual's study participation.

The tDCS device (NeuroConn DC Stimulator Plus Model 0021) comes with a list of pre-programmed five-digit numeric codes that are manually entered into the stimulator by the study team member at the time of an individual's study participation. These codes cause the device to deliver either active or "pseudo stimulation" (i.e., sham stimulation). Pairs of two codes (one active, one sham) for each participant will be aggregated by a study statistician who will then provide these pairs, and their order of administration, to a member of the study team in a way that the stimulation condition is not known (i.e., only the numeric codes and administration order will be relayed, not the key linking the codes to the stimulation condition).

All participants will be asked whether they thought that they received active or sham stimulation during each wave. This will take place at the end of the fifth day of the final study wave as part of the side effects questionnaire.

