7.5.3 Cognitive tasks during stimulation

During each stimulation session under both active and sham tDCS conditions, participants will engage in a computerized working memory n-back task that continuously adapts to the performance of the individual, remaining equally engaging and demanding over the course of training and across individuals of varying working memory ability ^{45,46}.

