7.6.2 Tools to Assess Primary and Secondary Endpoints

The primary and secondary endpoints will be assessed at the beginning and end of each five-day study wave in-person (i.e., subjective cognition and fatigue), and approximately seven days after the last stimulation session by phone (i.e., subjective cognition and fatigue). In-person testing will take approximately 20 minutes; whereas, testing via phone will take approximately 10 minutes.

- 7.6.2.1 Paced Auditory Serial Attention Test (PASAT)^{1,2}. The primary measurement tool for assessing objective cognitive functioning will be performance on the PASAT.

The PASAT is working memory task that has been well-validated medical populations including breast cancer⁵³. Test administration involves the aural presentation of single digits via computer in order to ensure a standardized rate of stimulus presentation. Stimuli are presented every three seconds (trial 1) or every two seconds (trial 2). Participants add each new digit to the one immediately prior as the test continues to

present stimuli. The test score reflects the total number of correct sums given (out of 60 possible) in each trial.

Two equivalent, alternative PASAT forms will be used to minimize practice effects. The test takes approximately 10 minutes to complete. It will be completed prior to and following both five-day active anodal and sham stimulation conditions (i.e. on four occasions). Available data indicates that prior to adjuvant treatment, breast cancer patients with stage I-III disease score an average of 46.6 ± 11.2 on the PASAT trial 1 (3 second administration) and an average of 34.3 ± 10.1 on trial 2 (2 second administration)⁵⁴.

7.6.2.2 Functional Assessment of Cancer Therapy Cognitive Scale (FACT-Cog version 3)⁵⁵. The measurement endpoint for subjective cognition will be scores on the FACT-Cog, a 37-item self-report measure addressing cognitive difficulties and their effect on patient quality of life. The measure addresses six cognitive domains (memory, concentration, mental acuity, verbal fluency, functional interference, and multitasking). The questionnaire is easy to use and appropriate for individuals with a history of cancer of varying age groups and backgrounds.

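### No wave (period) term is pre-specified for the primary PASAT test or the mixed models, so any difference in gain between waves costs efficiency and shifts the estimate when completer sequences are unequal

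*Combined protocol and SAP*

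**What the plan says.** The primary outcome in section 12.1 is a difference of changes: "Our primary outcome variable reflects the difference between pre- and post-anodal stimulation compared to pre- and post-sham stimulation". Section 12.3 then gives the test: "The comparison between active tDCS and shame stimulation in change in PASAT score will be performed using a two-sided paired t-test", restricted to participants who finish both waves. A PASAT mixed model that also takes in participants with only one completed wave is named, but no covariates are listed for it. For the secondary and exploratory mixed models the only commitment is that "the covariates will include the indicator of the stimulation condition". Order appears once, as an option: "Other covariates in the exploratory analyses may include but not be limited to the order of the experiments (for assessing carryover effects". No section names wave or period as a model term.

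On allocation, section 7.4 says that "participants will be randomized to receive active or sham tDCS during the first five-day study wave". It gives no ratio, blocking or balance of sequences. On attrition, section 12.2 says "we expect to enroll 50 breast cancer patients, with the expectation that 5 may not complete the crossover experiments".

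Three places bear on whether gains could differ between waves. Section 7.6.2.1 says "Two equivalent, alternative PASAT forms will be used to minimize practice effects", and the test is given four times. Section 7.5.3 says that in each session of both waves "participants will engage in a computerized working memory n-back task that continuously adapts to the performance of the individual". Section 5.2.1 reports modest practice gains under sham in a five-patient multiple sclerosis pilot.

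**The concern.** In a two-period crossover each participant's active-minus-sham difference contains the treatment effect plus or minus any period effect, with the sign set by sequence. Here the outcome is already a within-wave change. If everyone simply starts wave 2 at a higher level, that cancels. What does not cancel is a different amount of improvement within the two waves, for example a large practice gain in wave 1 and a small one in wave 2, after a week of working-memory training and two earlier exposures to the PASAT.

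A plain paired t-test leaves such a difference in its residual. With balanced sequences the interval is too wide and the test is conservative. With unbalanced sequences part of the wave difference also enters the tDCS estimate. The order covariate is not a safeguard as written. Coded as sequence (one value per participant), it does not remove a wave effect. Coded as first or second wave on each row, it does. The text does not say which is meant, and it is optional either way.

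**Working it through.** **Inputs.** From section 12.2: 45 completers, 50 enrolled, two-sided 5%, d = 0.43, paired t-test. Assumed, because the documents are silent: the size of the wave difference, and 25/25 allocation where stated.

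**Plan's own figure.** The noncentrality is 0.43 × √45 = 2.88 on 44 df, which gives power of 80.5%. The stated figure of at least 80% reproduces.

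**Model.** Let delta = (mean wave-1 gain − mean wave-2 gain) / within-sequence SD of the active-minus-sham change. With that SD set to 1, the paired difference has mean tau + delta in active-first participants (n1) and tau − delta in sham-first participants (n2). Ignoring wave gives:

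- shift in the estimate = delta × (n1 − n2)/N
- variance seen by the test ≈ 1 + delta² × [1 − ((n1 − n2)/N)²]

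At 23/22 and delta 0.5 the variance is 1 + 0.25 × 0.9995 = 1.25, so the standard error is about 12% too large (√1.25 = 1.118).

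The wave-adjusted estimate is the simple average of the two sequence means, with pooled within-sequence variance on 43 df and effective n = 4/(1/n1 + 1/n2). Delta drops out.

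**Near balance, 23/22** (100,000 simulated trials per cell):

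| delta | unadjusted type I error | unadjusted power, d on within-sequence SD | unadjusted power, d on observed SD | adjusted power, d on observed SD |
|---|---|---|---|---|
| 0.25 | 4.4% | 79.6% | 82.2% | 82.7% |
| 0.50 | 2.9% | 75.7% | 84.9% | 88.5% |
| 0.75 | 1.5% | 67.8% | 87.8% | 94.1% |

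With d on the within-sequence SD, adjusted power is about 80.4% throughout and type I error is 5.0%.

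**Imbalance from the protocol's own attrition.** Assume 25/25 allocation and five dropouts at random. The hypergeometric probabilities, in either direction, are 65% for 23/22, 30% for 24/21 and 5% for 25/20. The shifts are 1/45, 3/45 and 5/45 of delta, that is 0.02, 0.07 and 0.11 delta. The mean absolute shift is (0.651 × 1 + 0.299 × 3 + 0.050 × 5)/45 = 0.04 delta.

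- 20 active-first and 25 sham-first, delta 0.5: shift = 0.5 × (−5/45) = −0.056 SD, which is 13% of 0.43. Power is 60% unadjusted and 80% adjusted; type I error is 4.0%.
- The mirror split, 25/20: shift +0.056 SD. Unadjusted power is about 84%, higher only because the estimate is displaced upward.
- 27/18, which needs unbalanced allocation: shift 9/45 = 0.20 delta, and type I error is about 6.5% at delta 0.5.

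**Averaged over simple randomisation**, delta 0.5: bias 0 and type I error 5.0%. Power is 71.5% against 79.6% adjusted (within-sequence SD), or 80.9% against 87.7% (observed SD).

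**Mixed model.** For 25/20 completers, the expected shift is 0.111 delta with condition only, 0.111 delta with sequence added, and 0 with wave. Now take the extreme case of 20/25 completers plus five active-first participants with wave 1 only. The shift is −0.056 to −0.083 delta with condition only (assumed correlation of change scores 0 to 0.5), −0.059 to −0.086 with sequence added, and 0 with wave. With zero correlation this can be checked by hand: 25 of 50 active rows and 25 of 45 sham rows come from wave 1, and 0.500 − 0.556 = −0.056.

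**Cost of the term if there is no wave effect.** Adjusted power is 80.5% at 23/22, 80.0% at 25/20 (effective n 44.4) and 78.9% at 27/18 (effective n 43.2), against 80.5% unadjusted.

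**The case against.** The strongest reply is that everything hangs on delta, which the documents neither establish nor size. The cited sections support practice effects in general, not unequal gains between waves. The alternate forms and the adaptive task are there to limit the problem, and the pilot compares no waves. Deltas of 0.5 and 0.75 exceed the whole target effect of 0.43; at 0.25 and 23/22 the loss is about one power point. This stands, and it is why the sizes above are a range and not a prediction.

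Next, validity is largely kept: the test is conservative near balance, unbiased with 5.0% error over simple randomisation, and exceeds 5% only at a split such as 27/18. The typical attrition-driven shift at delta 0.5 is 0.02 SD, about 5% of the target effect and about one seventh of the standard error (1/√45 = 0.149). The 20/25 and five-dropout cases are extremes: the 5% covers both directions, so the adverse one is about 2.5%. This also stands. It makes the point mainly one about efficiency, and about the single split that will be reported.

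Third, section 12.2 ties d to the paired t-test, so d may be meant on the observed SD. Then power at 23/22 does not fall below plan. That is correct, but the adjusted test is still the more powerful on that reading.

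Last, order is named and the covariate list is open, so wave is unspecified, not excluded. True, but an optional, uncoded exploratory term gives no protection to the primary result, and choosing it after seeing data would be an unplanned decision.

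**Conclusion.** The concern holds. The primary test and the mixed models carry no pre-specified wave term in a crossover whose outcome is open to practice and training. It should be fixed, though it does not invalidate the trial. If gains do not differ between waves, nothing is lost. If they differ by 0.25 to 0.75 within-sequence SD, the unadjusted test at 23/22 gives up between under 1 and about 13 power points on that SD scale (80.4 − 79.6 to 80.4 − 67.8), or 0.5 to about 6 points on the observed-SD scale. The estimate moves by 0.02 to 0.11 delta under the protocol's expected attrition, and by more only if allocation is itself unbalanced, which section 7.4 leaves open. These sizes rest on assumed deltas, no carryover, and dropout unrelated to sequence. That the term is missing is certain; how much its absence matters is not.

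**What to change.** Before unblinding, amend section 12.3:

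1. Make the primary test the period-adjusted crossover comparison. Compute the active-minus-sham change for each completer, average the two sequence-specific means with equal weight, and take the standard error from the pooled within-sequence variance on 43 df. In completers this corresponds to a model of change on condition and wave with a random participant effect (provided the participant variance estimate is not negative). It is not identical to the PASAT mixed model that also includes one-wave participants.
2. List wave (first or second) as a fixed effect in the PASAT mixed model and in all secondary mixed models, including those for the day-7 phone scores.
3. State how order is coded, and keep it distinct from wave.
4. Keep the plain paired t-test as a sensitivity analysis.

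It would also help to state in section 7.4 whether sequence allocation is balanced, since that bounds the possible shift.

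The cost is one paragraph and one degree of freedom (43 instead of 44), with no extra patients or data. With no wave effect, the loss of power is about 0.1 point at 23/22, 0.5 at 25/20 and 1.7 at 27/18.
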